### 8.1 Visit 1/Screening

Screening procedures will be conducted by the Investigator, or suitably qualified designee.

The following screening procedures will be completed, in the following order (wherever possible), and the findings recorded in the CRF. To facilitate subject flow, clinical assessments may be recorded on a paper source document and later transcribed into the CRF.

1. Informed Consent.
2. Demographics.
3. Review of medical history (including smoking/tobacco use status) and prior/concomitant medication/treatment.
4. OST and OHT examinations.
5. Assessment of tooth color and extrinsic tooth stain.
6. For subjects with a self-reported history of DH, assessment of DH, including EAR, MGI and tooth mobility assessments and Evaporative (Air) Sensitivity Assessment (Schiff sensitivity score).
7. Review of the inclusion/exclusion criteria.
8. Subject eligibility assessed. Subjects who do not meet the criteria for participation will be discontinued.
9. Qualifying subjects will be stratified and randomized to treatment groups.
10. Subject completes the tooth sensitivity questionnaire at site.
11. Study products will be dispensed, including sundry items, and diary.
12. Instruct subject in product usage requirements/diary completion and demonstrate dispensing ribbon of dentifrice on to toothbrush head; supervise first brushing and first diary entry.
13. AEs and incidents recorded.

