### 12.3.1 Primary Analysis

The primary efficacy variable is mean Vita Bleachedguide shade at 24 weeks after tooth bleaching has completed, calculated at the subject level as the average Vita Bleachedguide shade over all sites assessed. The primary comparison will be the test dentifrice vs. the reference dentifrice. As there is only a single primary objective, no adjustment for multiple comparisons is required.

Mean Vita Bleached guide shade will be analyzed using a repeated measures ANOVA model with treatment group and time point as factors, and treatment group by time point as interaction. The adjusted mean treatment difference at 24 weeks will be obtained from the model and presented, along with 95% confidence intervals (CIs) and p-values. All p-values presented will be two-sided and assessed at the 5% significance level.

The assumption of normality and homogeneity of variance in the ANOVA will be investigated. In case of violation of these assumptions, a suitable nonparametric test will be performed; inferences drawn from non-parametric analysis will be considered as confirmatory results.

Summary statistics including mean, SD, standard error (SE), median, minimum, maximum will be provided by visit and randomized treatment group. Raw means and SE will also be plotted over time by treatment group.

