### **4 Data Analysis**

Data analysis will be performed by CCI with oversight from Haleon. The statistical analysis software used will be SAS version 9.4 or higher.

Prior to database closure a BDRM will be conducted in which various aspects of the trial will be discussed and agreed.

One aspect that will be considered prior to or during the BDRM is the assessment of the number of subjects who have dropped or discontinued from the study due to pandemic related events

and the potential need of a sensitivity analysis. Any major changes to planned analyses will need an amendment to SAP.

Except as described below, all listings will be produced for all randomized subjects.

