##### 4.4.1.2 Statistical Hypothesis, Model, and Method of Analysis

The primary comparison is between the Test Dentifrice and the Reference Dentifrice in the mITT population. As there is only a single primary objective, no adjustment for multiple comparisons is required.

Study product differences will be tested under the null hypothesis at 24 weeks after tooth bleaching has completed:

- $H_0$ : there is no difference in mean VITA shade score between Test Dentifrice and Reference Dentifrice
- $H_1$ : there is a difference in mean VITA shade score between Test Dentifrice and Reference Dentifrice

Mean VITA Bleached guide shade will be analyzed using a repeated measures ANOVA model with treatment group and study time points (Visit 2 to 5) as factor and treatment group by time point (Visit 2 to 5) as interaction. Subject will be included as a repeated measure with unstructured covariance matrix; the Kenward Rogers degrees of freedom approach will be

applied (Kenward and Roger, 1997). If the model with unstructured covariance matrix does not converge then compound symmetry covariance matrix will be used.

Using the above model, mean differences between Test Dentifrice compared to Reference Dentifrice in Mean VITA shade score will be reported by study product group along with 95% CIs and p-values will be provided in Table 14.2.2.2.1. All p-values presented will be two-sided and assessed at the 5% significance level.

The assumption of normality and homogeneity of variance in repeated measures ANOVA will be investigated. In case of violation of these assumptions, a suitable nonparametric test (Van Elteren Test adjusted for randomization stratification) will be performed, and the results will be provided to support the repeated measures ANOVA results. The non-parametric results will be considered confirmatory under the observation of strong violations of the assumptions.

If there is more than 10% difference in the overall number of subjects between PP and mITT populations, a summary and analysis of the primary efficacy variable will be presented for the PP population in Table 14.2.2.1.2 and Table 14.2.2.2.2 respectively.

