###### **4.4.2.1.1 Statistical Hypothesis, Model and Method of Analysis**

Study product differences will be tested under same hypothesis stated in [Section 4.4.1.2](#). Mean VITA Bleached guide shade will be analyzed using a repeated measures ANOVA model with treatment group and study time points (Visit 2 to 5) as factor and treatment group by time point (Visit 2 to 5) as interaction. Subject will be included as a repeated measure with unstructured covariance matrix; the Kenward Rogers degrees of freedom approach will be applied (Kenward and Roger, 1997). If the model with unstructured covariance matrix does not converge then compound symmetry covariance matrix will be used.

Refer to [Section 4.4.1.2](#). Mean differences between Test Dentifrice compared to Reference Dentifrice in Mean VITA shade score at 12 weeks after tooth bleaching will be presented along with 95% CIs and p-values in Table 14.2.2.2.1. All p-values presented will be two-sided and assessed at the 5% significance level.

The assumption of normality and homogeneity of variance in repeated measures ANOVA will be investigated. In case of violation of these assumptions, a suitable nonparametric test (Van Elteren Test adjusted for randomization stratification) will be performed to assess comparisons (Test Dentifrice vs. Reference Dentifrice at Week 12) and the results will be provided to support

the repeated measures ANOVA results. The non-parametric results will be considered confirmatory under the observation of strong violations of the assumptions.

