##### **4.4.2.2.1 Statistical Hypothesis, Model and Method of Analysis**

The results for mean total MLSI Area x Intensity (AxI), mean total MLSI (AxI) for gingival sites (AxI), mean total MLSI (AxI) for interproximal sites (AxI), mean total MLSI (AxI) for body sites (AxI), mean total MLSI Area (A), and mean total MLSI Intensity (I) will be obtained from the Repeated Measures ANOVA detailed in Section 4.4.1.2. Mean differences between Test Dentifrice compared to the Reference Dentifrice in mean Total MLSI (A×I) score at 12 and 24 weeks after tooth bleaching will be presented along with 95% CIs and p-values in Table 14.2.3.2 for all subjects in the mITT population. Significance testing will be conducted at the two-sided 5% significance level. Study product differences for each of the aforementioned efficacy variables will be tested under the null hypotheses described below at 12 and 24 Weeks:

- **Total MLSI (Area (A) x Intensity (I))**

H0: there is no difference in mean total MLSI Area x Intensity (A×I) scores between Test Dentifrice and Reference Dentifrice;

H1: there is a difference in mean total MLSI Area x Intensity (A×I) scores between Test Dentifrice and Reference Dentifrice;

Descriptive statistics (n, mean, SD, Standard Error [SE], median, minimum, and maximum) will be presented for Mean Total MLSI (AxI) score at each assessment time point in Table 14.2.3.1 for all subjects in mITT Population by study product. Raw mean  $\pm$  (SE) of mean Total MLSI (AxI) score at each timepoint will be plotted by study product in Figure 14.2.2.1 for all subjects in the mITT population.

- **Gingival sites (AxI)**

H0: there is no difference in mean MLSI (AxI) scores for gingival sites between Test Dentifrice and Reference Dentifrice;

H1: there is a difference in mean MLSI (AxI) scores for gingival sites between Test Dentifrice and Reference Dentifrice;

- **Interproximal sites (AxI)**

H0: there is no difference in mean MLSI (AxI) scores for interproximal sites between Test Dentifrice and Reference Dentifrice;

H1: there is a difference in mean MLSI (AxI) scores for interproximal sites between Test Dentifrice and Reference Dentifrice;

- **Body sites (AxI)**

H0: there is no difference in mean MLSI (AxI) scores for body sites between Test Dentifrice and Reference Dentifrice;

H1: there is a difference in mean MLSI (AxI) scores for body sites between Test Dentifrice and Reference Dentifrice;

- **MLSI (A)**

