#### **4.4.3.3 Exploratory Efficacy Variable 3**

The exploratory endpoint 3 will be change in mean VITA shade score from pre to post bleaching Treatment.

Descriptive statistics (n, missing, mean, SD, standard error [SE], median, minimum, and maximum) will be presented for mean VITA shade score at visit 2 (pre bleaching) and visit 3 (post bleaching) together with change from Visit 2 to Visit 3 will be presented in Table 14.2.4.3 for all subjects in the mITT population by study product group.

The results for this endpoint will be analyzed from an ANCOVA model where study product group will be fixed effect and mean VITA shade score prior to the start of tooth bleaching fitted as a covariate.

Using the above model, least squared mean, pairwise difference along with 95% CIs will be reported by study product in Table 14.2.4.4 for all subjects in the mITT population. Significance testing will be conducted at the two-sided 5% significance level.

The assumption of normality and homogeneity of variance in will be investigated. In case of violation of these assumptions, a suitable non-parametric test (Van Elteren) will be performed, and results will be provided to support the parametric results.

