#### **4.4.4 Handling of Missing Values/Censoring/Discontinuations**

Missing data will not be replaced or imputed. Subjects who withdraw from the study prematurely will be included in the statistical analyses up to the point of discontinuation.

The use of repeated measures analyses accounts for missing data assuming a missing at random assumption, i.e., there is a systematic relationship between the propensity of missing values and the observed data, but not the missing data.

It is therefore assumed that a subject with missing data would have obtained a similar efficacy result compared to a subject using the same study product with similar non-missing results at other timepoints (Baseline and the other post-Baseline visit).

Sensitivity analyses may be added to the SAP prior to unblinding in case of high drop-out rates and/or exclusion from PP analyses.

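### The primary model leaves out the shade measured before randomisation, and the DH stratum; adding both before unblinding needs no new data, but the gain in precision is unknown and no power shortfall is shown

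*SAP*

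**What the plan says.** The SAP's primary analysis (4.4.1.2) is a "repeated measures ANOVA model with treatment group and study time points (Visit 2 to 5) as factor", with the interaction of the two, an unstructured covariance and Kenward-Roger degrees of freedom. Protocol 12.3.1 agrees: "using a repeated measures ANOVA model with treatment group and time point as factors, and treatment group by time point as interaction". Neither lists a covariate or the stratum.

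The Week 12 shade analysis (SAP 4.4.2.1.1) repeats the model: "Mean VITA Bleached guide shade will be analyzed using a repeated measures ANOVA model with treatment group and study time points". The stain results "will be obtained from the Repeated Measures ANOVA detailed in Section 4.4.1.2".

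The order of events at Visit 1 is set in Protocol 8.1. Shade is assessed at step 5. At step 9, "Qualifying subjects will be stratified and randomized to treatment groups". First use of the allocated dentifrice comes at step 12. Inclusion criterion 6b (Protocol 5.2) requires a mean shade of at least 13 at Visits 1 and 2, so every randomised subject should have a Visit 1 value.

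An earlier shade is adjusted for in one place only, the exploratory pre-to-post bleaching ANCOVA (SAP 4.4.3.3), with the "mean VITA shade score prior to the start of tooth bleaching fitted as a covariate". That is the Visit 2 value, taken after randomisation.

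DH status stratifies the randomisation (SAP 3.2). In the primary analysis it appears only in the fallback Van Elteren test.

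On withdrawals, SAP 4.4.4 says: "Subjects who withdraw from the study prematurely will be included in the statistical analyses up to the point of discontinuation".

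**The concern.** Success rests on a single comparison of shade at Week 24 (SAP 1.2). A measurement of the same quantity, on the same teeth, taken before randomisation is normally the most useful covariate for such a comparison. It reduces residual variance to the extent that it predicts the outcome, and it corrects for a chance difference between the arms at entry. Here it is collected and then not used.

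The presence of Visit 2 in the model may give the impression that a baseline is already accounted for. It is not. Visit 2 is about two weeks after randomisation, on allocated product, and the treatment-by-visit interaction gives each arm its own unconstrained Visit 2 mean. With complete data and an unstructured covariance, the model's Week 24 contrast is simply the raw difference between the two arm means.

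Leaving out the DH stratum is a separate and smaller matter. The fallback test respects the randomisation scheme and the main model does not.

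**Working it through.** **1. The plan's own figure.** Inputs: difference 1, SD 2, 80% power, 64 completers per arm, 20% dropout (SAP 1.4); two-sided 5% (SAP 4.4.1.2). SE = 2 × √(2/64) = 0.354. Non-centrality = 1/0.354 = 2.83 on 126 df, giving power 80.1%. With 63 per arm it is 79.5%. 128/0.8 = 160. The stated size reproduces.

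**2. Complete data with Visit 1 shade added.** The residual SD becomes 2 × √(1 − rho²), where rho is the Visit 1 to Week 24 correlation (assumed; not in the documents). At rho 0, estimating a useless covariate inflates the SE by √(1 + 1/124), and power on 125 df is 79.8%, a cost of about 0.3 points. Adding a DH term with no effect as well gives 79.5%. Simulation with 64 completers per arm gave type I error between 4.9% and 5.1% with and without adjustment.

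**3. With withdrawals kept up to discontinuation.** This is the fairer comparison, because the repeated-measures model already recovers something from partial data. From the documents: 80 randomised and 64 completing per arm. Assumed: 8 per arm lost after Visit 3 and 8 after Visit 4, SD 2 at every visit, and one common correlation rho between all visits. For each arm the information matrix is the sum, over the three dropout patterns, of n times the inverse covariance of the visits observed. The SE of the contrast is the square root of twice the Week 24 element of its inverse. For the adjusted model the covariance is taken conditional on Visit 1. Degrees of freedom are 126 and 125.

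| rho | SE as written | SE adjusted | Power as written | Power adjusted | Gain (points) |
|---|---|---|---|---|---|
| 0.3 | 0.348 | 0.334 | 81% | 84% | 3 |
| 0.5 | 0.341 | 0.300 | 83% | 91% | 8 |
| 0.6 | 0.336 | 0.276 | 84% | 95% | 11 |

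Applying the factor √(1 + 1/124) to the adjusted SE does not change these figures to the nearest percent.

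**4. Weaker correlation across bleaching.** Equal correlations suppose that Visit 1 predicts Week 24 as well as Visit 4 does, although bleaching lies between Visit 1 and Week 24. Suppose instead that visits on the same side of bleaching correlate 0.7 and visits on opposite sides correlate 0.2, 0.3 or 0.4 (assumed), with the same dropout pattern. Power then moves from 84.4% to 85.7%, 84.5% to 87.3% and 84.5% to 89.5%: gains of about 1, 3 and 5 points.

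**5. Chance imbalance at entry.** With 80 per arm and a Visit 1 SD of 2 (assumed), one standard error of the Visit 1 difference is 2 × √(2/80) = 0.32 shade, and the 95% limit is 1.96 × 0.316 = 0.62. The unadjusted Week 24 difference shifts by the slope of Week 24 on Visit 1 times the imbalance. At slopes of 0.3, 0.5 and 0.6, a one-standard-error imbalance shifts it by 0.09, 0.16 and 0.19 shade, and a 0.62 imbalance by 0.19, 0.31 and 0.37, against a planned difference of 1.

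**The case against.** The best case for leaving the model alone is that the gain may be small. Bleaching intervenes between Visit 1 and Week 24. The entry floor of 13 also narrows the Visit 1 range, which tends to lower the correlation; for illustration, cutting a normal distribution at its median would turn a correlation of 0.5 into 0.33 and 0.6 into 0.41. The model is valid as it stands and agrees with the protocol. Shade is summarised by arm at each assessment time point (SAP 4.4.1.1), so an imbalance at entry would at least be visible. All of this stands, and it is why the size is left open. It does not remove the case for adjusting, since the loss at rho 0 is about 0.3 points.

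Four stronger readings are tempting, and the documents do not support them.

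- *The trial is underpowered.* The calculation reproduces on its stated inputs. SAP 1.4 words the 2 as the SD accompanying a mean change. If it is read as a change SD with equal variances, the score SD is 2/√(2(1 − rho)), and unadjusted power with 64 completers per arm would be 91%, 80%, 71% or 58% at rho 0.3, 0.5, 0.6 or 0.7. That can fall on either side of 80% and turns on a correlation that is not given. It is a sample-size question, separate from this point.
- *Adjustment would add 4 to 14 points.* Setting complete-data adjusted power (84% to 94% at rho 0.3 to 0.6) against 80% gives that range, but it ignores what the plan already recovers from subjects who withdraw.
- *The result would be biased.* Leaving out a covariate measured before randomisation does not bias the contrast. This says nothing about other sources. Criterion 6b applies again at Visit 2, after two weeks on allocated product, and subjects who fail the continuance check are discontinued (Protocol 8.2.1). Whether that could differ by arm is a separate question.
- *Omitting the DH stratum loses precision.* Nothing in the documents says that DH status predicts shade.

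**Conclusion.** The point holds as an optional improvement. The primary and Week 12 shade models ignore a measurement taken before randomisation that should be complete, and Visit 2 does not stand in for it. The omission leaves the test valid and the planned 80% power intact on its stated inputs. What is given up is precision and protection against chance imbalance at entry.

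The size cannot be fixed from the documents. Over the assumptions shown it runs from a loss of about 0.3 points of power, through gains of 1 to 5 points if correlations across bleaching are 0.2 to 0.4, to 3, 8 or 11 points if all visits correlate equally at 0.3, 0.5 or 0.6. The balance favours adjusting: a small possible loss against a possibly useful gain. The DH stratum belongs in the model so that the analysis matches the randomisation, not because a gain is shown.

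**What to change.** Before unblinding, amend SAP 4.4.1.2 and 4.4.2.1.1 to add as fixed effects:

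- Visit 1 mean VITA shade;
- Visit 1 shade by visit, so that the slope may differ before and after bleaching;
- DH stratum.

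Do not use Visit 2 as the covariate: it follows allocated treatment and could absorb part of the treatment effect. Record the departure from Protocol 12.3.1 in SAP section 5, which at present reports no changes. The matching step for stain (Visit 1 MLSI score in 4.4.2.2.1) is optional; no gain has been quantified there.

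The cost is one SAP amendment, which section 4 calls for in any case: "Any major changes to planned analyses will need an amendment to SAP". No new data, visits or subjects are needed. The shade terms use four parameters in all over Visits 2 to 5, and the stratum uses one more. The change should be fixed in advance, because adding covariates to the primary model after unblinding would invite doubt about the result.

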### 5.2 Inclusion Criteria

An individual must meet all the following inclusion criteria to be eligible for enrolment into, and continuance in the study:

1. Subject provision of a signed and dated informed consent document indicating that the subject has been informed of all pertinent aspects of the study before any assessment is performed.
2. Subject is of either sex and any gender who, at the time of screening, is between the ages of 18-65 years, inclusive.
3. Subject is willing and able to comply with scheduled visits, and other study procedures and restrictions.
4. Subject in good general and mental health with, in the opinion of the investigator or medically qualified designee, no clinically significant or relevant abnormalities in medical history (for example, a medical condition confirmed to be causing xerostomia), or upon oral examination, that would impact the subject's safety, wellbeing or the outcomes of the study, if they were to participate in the study, or affect the subject's ability to understand and follow study procedures and requirements.
5. Subject who is willing and able to undergo at-home tooth bleaching with peroxide-containing treatment unsupervised.
6. Subject with generally good oral health that fulfil all of the following:
  - a. Teeth suitable for peroxide bleaching and gradable for tooth color and suitable for MLSI evaluation with no significant defects, calculus, restorations, crowns or veneers that could impact peroxide tooth bleaching performance or study evaluations as judged by the clinical examiner.
  - b. Facial surfaces of maxillary anterior 6 teeth (tooth numbers 6-11) [Universal tooth number system] with mean Vita Bleachedguide shade  $\geq 13$  at Visits 1 and 2
  - c. Having no lesions of the teeth or oral cavity that could interfere with the study evaluations.

Property of Haleon- Confidential

May not be used, divulged, published or otherwise disclosed without the consent of Haleon

- d. Having a minimum of 16 natural teeth.

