### 1.4 Sample Size Calculation

There were no previous directly comparable studies that have evaluated the effect of dentifrice on maintaining tooth whiteness after peroxide bleaching upon which to base an estimate of sample size. However, based on a previous study evaluating the tooth whitening abilities of the test dentifrice ([Haleon Clinical Study 300024, 2023](#)), a mean change (SD) of VITA scores of 1 ( $\pm 2$ ) was assumed. Sufficient individuals will be screened to enroll approximately 160 subjects (approximately 80 per group) assuming an estimated 20% dropout rate; approximately 128 completed subjects (approximately 64 per group) are deemed sufficient to detect a difference between the Test and Reference Dentifrices at 24 weeks with 80% power.

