#### 4.4.1 Primary Efficacy Endpoint

##### 4.4.1.1 Primary Efficacy Endpoint Definition

The primary efficacy variable is mean Vita Bleached guide shade at 24 weeks after tooth bleaching has completed, calculated at the subject level as the average Vita Bleached guide shade over all sites assessed.

Tooth color of the facial surfaces of the six anterior maxillary teeth (tooth numbers 6-11) [Universal tooth numbering system] will be assessed by a single, trained clinical examiner using the VITA Bleached guide 3D-MASTER. The VITA Bleached guide 3D-MASTER uses a value-ranked ordered scale from 1 (the lightest) to 29 (the darkest). The shade level of each tooth surface is scored visually by the clinical examiner with reference to the Bleached guide.

The mean VITA shade score for each subject at each visit is calculated as the mean VITA shade score over all non-missing facial surfaces of six anterior maxillary teeth (tooth numbers 6-11).

Descriptive statistics (n, missing, mean, SD, standard error [SE], median, minimum, and maximum) will be presented for mean VITA shade score at each assessment time point in Table 14.2.2.1.1 for all subjects in the mITT population by study product.

Raw means ( $\pm$  SE) of the mean VITA shade score at each time point will be plotted by study product in Figure 14.2.1.1 for all subjects in the mITT population.

Individual data for mean VITA shade score will be listed for each subject by study product group and visit in Listing 16.2.6.1 for all randomized subjects.

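### If the unstructured model fails, the SAP falls back straight to compound symmetry, and the Week 12 and Week 24 standard errors may then be biased in either direction.

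*SAP*

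**What the plan says.** SAP 4.4.1.2 analyses mean VITA shade with treatment group, visit and "treatment group by time point (Visit 2 to 5) as interaction". Visit 2 (before bleaching) is therefore a modelled response alongside Visit 3 (end of bleaching), Visit 4 (12 weeks) and Visit 5 (24 weeks). The covariance is unstructured, and "the Kenward Rogers degrees of freedom approach will be" applied. The only contingency is: "If the model with unstructured covariance matrix does not converge then compound symmetry covariance matrix will be used". No intermediate structure and no robust standard error is named.

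SAP 4.4.2.1.1 repeats the rule for shade at 12 weeks. Under SAP 4.4.2.2.1 the six MLSI outcomes "will be obtained from the Repeated Measures ANOVA detailed in Section 4.4.1.2", so they take the same fallback.

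Protocol 5.2 admits and continues only subjects "with mean Vita Bleachedguide shade" of at least 13 at Visits 1 and 2. No such limit applies at Visits 3 to 5. SAP 1.4 gives one SD for shade, 2, with no values by visit and no correlations.

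**The concern.** For four visits an unstructured matrix has 4 × 5 / 2 = 10 parameters. Compound symmetry has two: one variance and one correlation. The plan moves from one to the other in a single step.

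Under compound symmetry the treatment difference at any one visit borrows its variance from all four. There are two document-based reasons to doubt that the four variances are equal. The floor of 13 cuts off the lower end of the Visit 2 distribution only. Bleaching then takes place between Visits 2 and 3, and Protocol 2 describes the duration of the whitening benefit as patient-specific, which could widen the spread later on.

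Kenward-Roger does not help here. It corrects for small samples on the premise that the fitted structure is right. If the fallback were used and the variances differed, the standard error, confidence interval and p-value for the primary comparison, which is the sole success criterion, could be too optimistic or too pessimistic. The same holds for shade at Week 12 and for MLSI at both times.

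**Working it through.** **The plan's own figure.** With a difference of 1, SD 2, two-sided 5% and 80% power (SAP 1.4 and 4.4.1.2), the normal approximation gives 2 × (1.960 + 0.842)² × 2² / 1² = 62.8, so 63 per group. The noncentral t gives 80.1% power at 64 per group. Allowing for 20% dropout, 128 / 0.8 = 160. The stated sample size reproduces and is not at issue.

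**Formula for the fallback.** With complete, balanced data and a full treatment-by-visit mean model:

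- pooled SD = √(mean of the four visit variances)
- standard error under compound symmetry = pooled SD × √(2/n)
- true standard error at a visit = SD at that visit × √(2/n)
- ratio R = pooled SD / SD at that visit
- actual type I error = 2 × [1 − Φ(1.96 × R)]

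Worked example, SDs 1.5/2/2/2 at Visits 2 to 5: mean variance = (2.25 + 4 + 4 + 4)/4 = 3.5625; pooled SD = 1.8875; R = 1.8875/2 = 0.944; type I error = 2 × [1 − Φ(1.850)] = 6.4%. With 64 per group, √(2/64) = 0.1768, so the reported standard error is 0.334 against a true 0.354.

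**Results for shade.** All visit SDs are assumptions.

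| SDs, Visits 2/3/4/5 | Pooled SD | R, Week 24 | Type I error, Week 24 | Type I error, Week 12 |
|---|---|---|---|---|
| 2/2/2/2 | 2.000 | 1.000 | 5.0% | 5.0% |
| 1.5/2.4/2/2 | 2.001 | 1.000 | 5.0% | 5.0% |
| 1.5/2.5/2.25/2 | 2.095 | 1.048 | 4.0% | 6.8% |
| 1.5/3/2.5/2 | 2.318 | 1.159 | 2.3% | 6.9% |
| 1.5/2/2/2 | 1.887 | 0.944 | 6.4% | 6.4% |
| 1.5/2/2.2/2.5 | 2.082 | 0.833 | 10.3% | 6.4% |
| 1.2/2/2.5/3 | 2.274 | 0.758 | 13.7% | 7.5% |

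In the 1.5/3/2.5/2 row, power at Week 24 for a difference of 1 is about 71%, compared with 81% by the same normal approximation when the standard error is right. The same row is conservative at Week 24 and anti-conservative at Week 12.

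**MLSI, illustration only.** The documents give no MLSI SDs. Assumed SDs of 0.6/0.2/0.5/0.8 give a pooled SD of √(1.29/4) = 0.568 and type I error of 16% at Week 24 and 2.6% at Week 12.

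**How far the floor alone goes.** If Visit 2 shade were normal with SD 2 before truncation at 13, the SD left would be 1.21 for a mean of 13, 1.59 for a mean of 15 and 1.96 for a mean of 18. The floor matters if it lies near the mean and hardly at all if it does not.

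**Check with dropout.** The formula assumes complete data, so it was compared with a REML simulation: 80 per group, 20% missing at Week 24 at random, correlation 0.6, t reference without the Kenward-Roger correction.

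- SDs 1/1.5/1.75/2: mean compound-symmetry standard error 0.265 against an empirical 0.327; rejection 10.1% against 3.9% unstructured (1,000 runs; the formula gives 11.6%).
- SDs 1.2/2/2/2: 0.306 against 0.344; rejection 9.2% against 6.7% unstructured (1,000 runs).
- SDs 1.5/3/2.5/2: 0.395 against 0.328; rejection about 1.3% (400 runs).
- Equal SDs: 0.336 against 0.343, so no material distortion (400 runs).

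Direction and rough size agree with the formula.

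**The case against.** **The rule will probably not be used.** Ten covariance parameters from about 128 to 160 subjects is an easy fit. This stands, and it is why the point ranks low. A reader might infer that MLSI changes this, because stain near zero after bleaching could make the covariance almost singular. The documents do not support that. They give no MLSI distribution after bleaching, and a small variance at one visit is a difference of scale, not singularity. In a REML check with 160 subjects, 20% dropout and assumed correlations of 0.5 to 0.6, including MLSI-like scores with about 89% exact zeros at Visit 3, the unstructured fit converged in 500 of 500 runs. That used a general optimiser rather than SAS, on assumed inputs.

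**There is already a safeguard.** SAP 4.4.1.2 has normality and homogeneity of variance investigated, with a Van Elteren test if they are violated. A test at Week 24 alone does not depend on the covariance across visits, so this counts, but only in part. For shade it becomes confirmatory only under strong violations, a term the SAP does not define. For MLSI (SAP 4.4.2.2.1) it is supportive only. It also yields no adjusted mean difference or confidence interval, which are the planned results.

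**The fallback is at least fixed in advance.** True, and that prevents a choice of covariance after unblinding. An ordered list keeps that advantage. Heterogeneous structures still constrain the correlations, so they are an improvement and not a guarantee.

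**Conclusion.** The point holds as a low-severity improvement. If the fallback is used, the Week 12 and Week 24 standard errors rest on the variance averaged over Visits 2 to 5, and they are biased unless that average happens to equal the variance at the visit in question. For shade at Week 24 the patterns tried give type I error from 2.3% to 13.7%. Those figures rest on assumed visit SDs and on complete data; they show what is possible and are not a forecast.

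Two stronger readings are tempting. One is that the visit variances must differ, so the standard error is wrong whenever the rule is invoked. The documents give no SD by visit, a floor well below the mean barely changes the Visit 2 SD, and SDs of 1.5/2.4/2/2 are unequal yet leave the Week 24 error at 5.0%. The other is that the rule inflates type I error. Patterns that peak at Visit 3 are equally compatible with the documents and are conservative at Week 24. Neither reading is supported. The sample size and the main unstructured analysis are unaffected.

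**What to change.** Replace the fallback sentence in SAP 4.4.1.2 and 4.4.2.1.1 with an ordered list that keeps a separate variance for each visit:

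1. unstructured (10 parameters);
2. heterogeneous Toeplitz (4 variances + 3 correlations = 7);
3. heterogeneous compound symmetry (4 + 1 = 5).

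Use the first that converges, with Kenward-Roger degrees of freedom. Allow homogeneous compound symmetry only as a last resort and with a sandwich standard error, and name the degrees-of-freedom method for that case, since Kenward-Roger belongs with the model-based standard error. The MLSI analyses in SAP 4.4.2.2.1 pick up the change by reference.

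The cost is one sentence in two places before unblinding. No extra data or tables are needed, and no extra work arises unless the unstructured fit fails.
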